1.2 Schedule of Activities (SoA)

Schedule of Activities

Procedures	Screening	Office	Home
Telephone or outpatient contacts with participant	X		
Informed consent when patient comes to office		X	
Analysis of CPAP compliance data		X	
Demographics		X	
Medical history & medications		X	
Height		X	
Weight		X	
Randomization		X	
Provide equipment and training		X	
1 st Post- 6-Week Activity			
Review and confirm eligibility criteria	X		
ESS			X
FOSQ			X
AE/SAE Monitoring			X

2 nd Post- 6-Week Activity			
ESS			X
FOSQ			X
AE/SAE Monitoring			X
Return study equipment		X	
Receive future home therapy equipment and training		X	

Abbreviations: AE = adverse event; ESS = Epworth Sleepiness Scale; FOSQ = Functional Outcomes of Sleep Questionnaire; PROMIS = Patient-Reported Outcomes Measurement Information System; SAE = serious adverse event

2 Introduction

2.1 Study Rationale

A device able to provide inspiratory positive airway pressure (PAP) < expiratory PAP, designated TPAP, is being developed by SleepRes for the treatment of obstructive sleep apnea (OSA). In prior studies, the administration of higher inspiratory than expiratory PAP did not substantially increase treatment efficacy or adherence to continuous PAP (CPAP), which remains low. In our recent investigation, we demonstrated that the addition of a resistor to the CPAP circuit to reduce inspiratory PAP increased subjective comfort. The present study, TheraPAP Adherence, is a Crossover study designed to examine whether TPAP can improve adherence over CPAP as an at home treatment for OSA.

2.2 Background

2.2.1 Obstructive Sleep Apnea

The National Commission on Sleep Disorders Research identified sleep disorders as a major public health burden. OSA is the most common of the more serious sleep disorders and affects approximately 20 million people in the United States (US), with approximately 13% of men and 6% of women affected (1). OSA is characterized by repetitive collapse or ‘obstruction’ of the pharyngeal airway during sleep, manifesting as repetitive episodes of hypopnea (i.e., shallow breathing) or apnea (i.e., paused breathing). These episodes of hypopnea or apnea may lead to hypoxemia, arousal from sleep, sleep fragmentation, excessive daytime sleepiness, and/or neuropsychological impairment.

Long-term, OSA is associated with increased mortality and a number of adverse cardiovascular, neurocognitive, metabolic, and daytime functioning consequences (2-11).

2.2.2 Unmet Medical Need

The large majority of OSA patients are treated with positive airway pressure, the most common of which is CPAP, provided by a machine that mechanically maintains an open airway. However, long-term adherence to therapy remains a challenge for many patients (12, 13). Common complaints include inconvenience, lack of perceived benefit, discomfort related to improper fitting of the interface, and difficulty expiring against positive pressure (14, 15).

As many patients cannot use CPAP because they find it intolerable, this represents a significant health concern, as OSA is associated with numerous adverse health outcomes and increased mortality. Strategies to improve tolerance of CPAP, and subsequently adherence, are needed.

2.2.3 Biological Rationale

TPAP is an innovative device/algorithm designed to deliver a lower inspiratory than expiratory PAP. The drop in inspiratory pressure can be modulated during the inspiratory phase. Previous research has shown that reducing inspiratory PAP by placing a resistor in the inspiratory line can enhance subjective comfort and decrease leaks when compared to CPAP, despite maintaining a similar residual apnea-hypopnea index (AHI). However, the resistor could only provide a fixed inspiratory PAP reduction based on existing PAP settings. TPAP addresses this limitation by allowing for adjustable drops in inspiratory PAP throughout the inspiration phase, offering a potentially more personalized and adaptive therapeutic approach.

3 Endpoints

	Endpoints
Primary	
• Nightly adherence (usage) with device (TPAP versus APAP)
Secondary	
• Evaluation of P95, Leak and AHI over each 6-week period• 6-week Subjective Questionnaires (TheraPAP versus APAP) following each arm
◦ ESS◦ FOSQ• Adverse Event rate
Safety Endpoints²	
• Spontaneous adverse events

² Although there will not be any direct treatment vs. control comparison here, we will assume that CPAP is safe and that any abnormal value recorded in the next morning compared to the evening before the polysomnography is due to treatment with TPAP.

4 Study Design

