Within the TPAP arm, participants will be set to a double Comfort Setting drop according to the following table. This drop schedule will be implemented even while the TPAP device is operating with automatic pressure adjustment.

P _{set} (cmH ₂ O)	Pressure Drop 1 (cmH ₂ O)	Pressure Drop 2 (cmH ₂ O)
5.0 - 5.9	0	0
6.0 - 6.9	1	0
7.0 - 7.9	2	0
8.0 - 8.9	2	1
9.0 - 9.9	2	2
10.0 - 20.0	2	3

Table 1: Comfort Setting Pressure Drops 1 and 2 to be used at the specified target set pressure to the patient.

Participants will use their starting therapy nightly at home for 6 weeks after which time they will undergo a washout period of 1 week where no therapy will be used. Following the washout period, they will initiate another 6-week usage with the second therapy. Afterward, they will return to the office to receive their permanent equipment. Phone calls as reminders to end the first arm, start the washout period, then to start the second arm will be made.

Immediately after both arms of the study are completed, the following will occur:

- Eligibility criteria will be reviewed and confirmed
- Participants will be asked to respond to the following
 - ESS (Epworth Sleepiness Scale)
 - FOSQ (Functional Outcomes of Sleep Questionnaire)

During the home use period, subjects will be called at the following time points during each arm of the study. At each time point, adverse events and compliance with the device will be assessed. Subjects using the device less than an average of 5 hours per night during the first week will be contacted on a more regular basis (weekly until 5 hour per night use is achieved) to address any problems and encourage use. If patients discontinue use of the device during the home use period, they will still be encouraged to return for all testing per protocol. If a patient refuses to come in for further testing, they will be considered a lost to follow up and excluded from efficacy analysis.

- 1 Day Phone Call (+2 days)
- 7 Day Phone Call (+/- 3 days)
- 14 Day Phone Call (+/- 3 days) IF deemed necessary per 7 Day compliance
- 28 Day Phone Call (+/- 3 days) Check-in

- Week 6 Phone Call (+/- 3 days) – End first arm, fill out questionnaires, start Washout Period
- Week 7 Phone Call (+/- 3 days) - Review protocol, start 2nd arm
- Week 12 (+/- 3 days) - Equipment Return

Data collected from the therapy device will include the following:

- Usage averaged over the 6-week period and nightly
- Leak averaged over the 6-week period and nightly

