6.2 Safety Assessments

Planned time points for all safety assessments are provided in the SoA.

Safety assessments will include measurement of vital signs, monitoring and recording of AEs, SAEs, and recording of study or treatment discontinuations. Effects on OSA and sleep parameters (e.g., sleep time and sleep stages) will also be monitored by PSG.

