6.3.1 Time Period and Frequency for Collecting AE and SAE Information

All AEs and SAEs will be collected from randomization until the end of the study at the timepoints specified in the SoA.

All SAEs will be recorded and reported to the Sponsor or designee within 24 hours, as indicated in Appendix 2. The Investigator will submit any updated SAE data to the Sponsor within 24 hours of it being available.

Investigators are not obligated to actively seek AEs or SAEs after the conclusion of study participation. However, if the Investigator learns of any SAE, including a death, at any time after a participant has been discharged from the study, and he/she considers the event to be reasonably related to the study or study participation, the Investigator must promptly notify the Sponsor.

The method of recording, evaluating, and assessing causality of AEs and SAEs and the procedures for completing and transmitting SAE reports are provided in Appendix 2.

Care will be taken not to introduce bias when detecting AEs and/or SAEs. Open-ended and non-leading verbal questioning of the participant is the preferred method to inquire about AE occurrence.

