7.3 Populations for Analyses

For the purposes of analysis, the following analysis sets are defined:

Set	Description
Randomized	All participants who were randomized.
Modified Intent to Treat (mITT) Set	The mITT set comprises all participants who are randomized, undergo at least 1 night in either study arm, and have at least 1 measurement on the primary endpoint. Participants will be analyzed for equivalence.
Safety Set	The Safety Set consists of all participants who are randomized and undergo at least 1 night in either study arm.
Per Protocol (PP) Set	The PP Population consists of all participants without any major protocol violations and have considered to be evaluable for study analysis.

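### Footnote 2 to the Safety Endpoints disclaims an adverse-event comparison that this crossover can make, and refers to polysomnography values that are not scheduled

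*Protocol*

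**What the plan says.** Section 3 (Endpoints) lists spontaneous adverse events as the only safety endpoint. Footnote 2, whose marker is on the Safety Endpoints heading, says "there will not be any direct treatment vs. control comparison here, we will assume that CPAP is safe", and adds that "any abnormal value recorded in the next morning compared to the evening before the polysomnography is due to treatment with TPAP". The Secondary row of the same table lists "Adverse Event rate" with no footnote and no stated contrast. The primary endpoint and the questionnaires, by comparison, are marked as TPAP or TheraPAP versus APAP.

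Other sections describe how adverse events are gathered:

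- Synopsis (1.1): participants are called at set times "during each arm of the study. At each time point, adverse events and compliance with the device will be assessed".
- Schedule of Activities (1.2): a row "AE/SAE Monitoring" appears after the first 6-week period and again after the second.
- Section 6.3.1: "All AEs and SAEs will be collected from randomization until the end of the study at the timepoints specified in the SoA".
- Section 7.3: "The Safety Set consists of all participants who are randomized and undergo at least 1 night in either study arm".

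Section 6.2 names vital signs and polysomnography among the safety measures and states "Planned time points for all safety assessments are provided in the SoA". The Schedule of Activities has a row for neither.

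**The concern.** A rule that assumes the control is safe and blames the new therapy for any overnight change would suit a study in which people are measured before and after a night in the laboratory on the new therapy only. This trial is a randomised crossover with 6 weeks of home use on each therapy, and its control period is observed as fully as its active period.

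What is at stake is the controlled safety contrast. Participants are new to PAP, so some events will come with starting any PAP therapy. APAP is delivered on the same S.Box, which section 4.2.5 says is CE-marked but has no 510(k). Comparing events by therapy is the direct way to separate general PAP or device events from events linked to the TPAP algorithm. Section 4.2.5 expects no risks from TheraPAP, and a by-therapy summary is the evidence in this trial that bears most directly on that expectation. AHI, leak and P95 are relevant but do not replace what participants report.

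**Working it through.** The plan gives no figure on this point to reproduce. The check is a side-by-side reading, followed by a calculation of how precise the comparison would be.

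**1. Is there a control period with adverse-event data?** Yes. Sections 1.1 and 4.1 give each participant 6 weeks on each therapy, with a 1-week washout between. The synopsis assesses events at calls in each arm, the Schedule of Activities monitors them after each period, section 6.3.1 collects them from randomisation to study end, and the Safety Set admits a night in either arm. The data for a by-therapy summary will exist.

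**2. Does the table give one consistent rule?** No. The Safety row carries a footnote ruling out a comparison. The Secondary row lists an adverse-event rate without that restriction and without a contrast. The protocol does not say how the two relate.

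**3. Can the attribution clause operate?** Not as scheduled. It needs evening and morning values around a polysomnography. In the design, polysomnography is a source of eligibility data from the 3 months before the study (section 4.1). Section 6.2 mentions it as safety monitoring but defers timing to the Schedule of Activities, which has no such row.

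**4. Does the clause agree with Appendix 2?** No. Appendix 2 requires the investigator to judge causality for each event, weighing alternative causes and timing, and counts clinically significant abnormal vital signs as adverse events. A blanket attribution to TPAP would collide with that if such values were ever taken.

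**5. How precise would the comparison be?** Take the within-participant difference in the proportion with at least one adverse event, with a true difference near zero:

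95% half-width = 1.96 × √(d / n)

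Here d is the proportion of participants who have an event on one therapy only. The protocol gives no value, so 10%, 30% and 50% are assumptions. The values of n come from the protocol: 32 enrolled (synopsis) with about 20% dropout (section 7.1), so 32 × 0.8 = 25.6, rounded down to 25; 28 (14 per sequence, section 7.1); 32 with no dropout; and 36 (section 7.1 plan) with no dropout.

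| n | d = 0.10 | d = 0.30 | d = 0.50 |
|---|---|---|---|
| 25 | 0.124 | 0.215 | 0.277 |
| 28 | 0.117 | 0.203 | 0.262 |
| 32 | 0.110 | 0.190 | 0.245 |
| 36 | 0.103 | 0.179 | 0.231 |

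For example, n = 25 and d = 0.50 gives 1.96 × √(0.50 / 25) = 1.96 × 0.1414 = 0.277. At n = 25 and d = 0.10 only 25 × 0.10 = 2.5 discordant participants are expected, so the normal approximation is rough there.

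**The case against.** The best defence is that the footnote changes little in practice. Its disclaimer applies only to the Safety row, the secondary adverse-event rate can be read as a rate by therapy, and the tabulation of adverse events is ordinary SAP content. The polysomnography clause has nothing to act on, looks carried over from another design (an inference), and in any case leans against the sponsor's own device. The data are collected whatever the footnote says.

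Much of this stands, and it limits the point. A reader might infer that adverse events will be reported for TPAP alone, or that the controlled safety contrast is lost. The documents support neither. The footnote forgoes a comparison but does not say that APAP events go unreported. The secondary endpoint leaves room for a by-therapy rate, and nothing in data collection prevents one.

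The appeal to the SAP does not fully answer the point. The protocol is not silent here; it says that no comparison will be made on its safety endpoint. A SAP that compared spontaneous events by therapy under that endpoint would depart from the protocol as written.

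It is also fair to say that the comparison would exclude only large differences, in a trial that section 7.1 calls exploratory. That argues for labelling it descriptive, not for ruling it out.

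**Conclusion.** The point holds as a wrongly stated rule of minor to moderate weight. Footnote 2 disclaims a comparison that the design supports, assumes the control is safe although it is observed, and refers to measurements that are not scheduled. It also fits poorly with the secondary endpoint and with Appendix 2. This conclusion rests on the text alone and needs no assumption.

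The half-widths of about 0.10 to 0.28 depend on the assumed discordance. They describe how imprecise a by-therapy comparison would be. They should not be read as the harm done by the footnote, which the documents give no means to quantify. The primary adherence endpoint and its sample size are unaffected.

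**What to change.** - **Section 3.** Delete footnote 2. State that each adverse event is attributed to the therapy in use at onset, that washout events are listed separately, and that events are summarised descriptively for TPAP versus APAP in the Safety Set. State that the secondary adverse-event rate is this by-therapy comparison.
- **Section 6.2 (separate item).** Remove the polysomnography sentence, since no on-study polysomnography is scheduled. For vital signs, the sponsor should decide: either add them to the Schedule of Activities or remove them from section 6.2. The documents do not show which was intended, and removal would drop a stated safety assessment.

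**Cost.** The change to section 3 is wording and adds no visits. The onset date of each event must be recorded; confirm that it is a CRF field. Adding vital signs would add measurements, and a change to stated safety assessments may need IRB approval under Appendix 1.

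**Downside.** The comparison is open-label and imprecise at about 25 to 36 participants. Participants averaging under 5 hours a night in the first week get extra calls (section 4.2.2), so opportunities to report events may differ by therapy if usage differs. It should be labelled descriptive.

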4.1 Overall Design

Safety issues regarding this study are detailed in Appendix 1: Regulatory, Ethical, and Study Oversight Considerations.

The TheraPAP Adherence 1 Study is a randomized, controlled, crossover study in PAP-naïve participants with OSA. Pre-screening is conducted to establish potential eligibility based on an in-lab polysomnogram (PSG), a PSG split-night PSG/titration or a home sleep study (HST) that has been conducted within the previous 3 months. Participants would then be recruited as described below. For those who consent, they will be given the equipment and instructions to complete both arms of the study but will have their therapy device set to the parameters necessary to start the first arm, which will be randomly assigned. They will use the device nightly for 6 weeks, after which they will use no therapy for 1 full week (washout period). During this washout period, their therapy device will be remotely set to their second arm. When they restart therapy, they will use the device nightly for a further 6 weeks. During each arm, various data will be remotely collected from their therapy device, and after completion of each arm, they will fill out 3 questionnaires and average data during the 6 weeks of that arm will be downloaded. Once all activities are completed, they will be eligible to receive the incentive pay and their involvement will be completed.

4.2 Detailed Design

4.2.1 Pre-Screening

The first phase of recruiting for the TheraPAP Adherence 1 study will be done during the phone follow up during which the patients will be scheduled to come to the office of Sleep Centers of Middle Tennessee (SCMT) to collect their CPAP equipment. The following regarding the study will be conveyed to them: goals, a summary protocol, risks/benefits, other activities required by them, financial compensation and timing. They will also be asked for verbal permission to review their records so that office personnel can conduct a preliminary screening for eligibility. If they agree and show interest based on the first phase, they will be added to the eligibility roster.

The second phase of recruiting will be conducted when they come into the office to pick up the equipment. The coordinator will review the material related to the study, as well as the details within the informed consent. If the patient agrees to continue, they will sign the informed

consent in ink and be enrolled in the study. The coordinator will conduct a final check that the patient satisfies all enrollment criteria. After this, they will be enrolled in the study.

They will then be randomly assigned to start in either the APAP or TPAP arms of the study, and their equipment will be set up by the coordinating staff to operate according to the randomly chosen arm. During this setup, the pressure range will also be set to 5-20 cmH₂O irrespective of study arm. They will receive this equipment for the study, then be given instructions for use on both arms both verbally and through material that they can take home.

4.2.2 First 6-Week Arm

Patients will start using their equipment the first night. The study coordinator will monitor usage nightly and after the third night with a minimum of 5 hours of use, they will remotely adjust the device pressure range to P95 ± 2 cmH₂O, using the P95 from the third night. This range will be used for the remainder of both arms of the study. During the study, daily remote collection of usage will be conducted both for later primary endpoint analysis and to guide further contact with the patient if they need help.

During usage in the first arm, P95 and AHI will be monitored to assure that the patient is receiving proper therapy. If P95 is near the upper limit and the AHI is above 5 events per hour, the range will be bumped up by 2 cmH₂O.

A contact schedule will also be set up with each patient to follow up on any needs for help. Similar interaction is customary with new CPAP patients. The schedule is as follows and will be conducted on both arms of the study:

- 1 Day Phone Call (+2 days)
- 7 Day Phone Call (+/- 3 days)
- 14 Day Phone Call (+/- 3 days) IF deemed necessary per 7 Day compliance
- 28 Day Phone Call (+/- 3 days)

Participants using the device less than an average of 5 hours per night during the first week will be contacted on a more regular basis (weekly until 5 hour per night use is achieved) to address any problems and encourage use. If patients discontinue use of the device during the home use period, they will still be encouraged to complete surveys per protocol. If a patient refuses to complete such surveys, they will be considered lost to follow up and excluded from efficacy analysis.

At the end of the 6-week period, patients will stop using any sleep therapy for 1 week as a washout between arms. The study coordinator will remotely switch the mode of operation of the

therapy device to that for the second arm employing the same pressure range as was used in the bulk of the first arm. Patients will be asked to fill out the questionnaires during this period (ESS and FOSQ). Additionally, the following data averaged over the 6-week period of the trial will be downloaded from the device:

- Usage
- Leak
- P95
- AHI

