1.1 Synopsis

Protocol Title: A Prospective, Randomized, Crossover Study of the TheraPAP Compared to Automatic Adjusting Positive Airway Pressure (APAP) for the Treatment of Obstructive Sleep Apnea (OSA)

Protocol Name/Number: TheraPAP Adherence 1

Sponsor: SleepRes, PLLC

Rationale: TheraPAP is a prototype device (with full documented electrical and isolation safety) being developed by SleepRes for the treatment of obstructive sleep apnea (OSA) that can deliver either standard CPAP at a set pressure or what is called TPAP¹. TPAP is a pressure control algorithm that lowers the pressure from the set pressure at the beginning of inspiration and does not return the pressure to the full set level until about halfway through expiration. The present study, TheraPAP Adherence 1, is a randomized crossover study designed to examine the difference in therapy adherence between TPAP vs. CPAP alone in the treatment of OSA.

Overall Design:

The TheraPAP Adherence Study is a randomized, crossover study in treatment naive participants with OSA in which the adherence to therapy will be compared between TPAP and standard APAP. Because all participants will breathe on both therapy types and those therapy types are individually unique in feel, blinding is not possible. Participants will be chosen from a pool of patients who are PAP-naïve and who have received either a PSG (in-lab polysomnogram), split-night study (in-lab PSG and pressure titration) or home sleep study (HST) within the previous 3 months.

Upon signing an informed consent, participants will be randomly assigned to start on either the TPAP or APAP arms when they arrive at the office to pick up their Sefam S.Box with TheraPAP algorithms integrated. Each participant will then be given their new equipment and will be trained in proper use for both arms of the study so that they will not need to appear at the office again until the study is completed. In both the APAP and TPAP arms, participants will have their therapy set to 5-20 cmH₂O for three nights. The pressure range will then be narrowed to ± 2 cmH₂O around their 95% pressure level as assessed during the third night. This same pressure range will be used during the second arm for each patient.

¹ TPAP will be used herein to refer to the active treatment.

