4.2.3 Second 6-Week Arm

Following the one-week washout period, patients will start the second arm therapy for the next six weeks of nightly use. The procedure will be exactly the same as for the first arm, described above except that the device pressure range will be retained at the same settings that were present during the bulk of the first arm.

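### The pressure range is called fixed for both arms, yet it can be raised in the first arm only and is carried over by an undefined 'bulk' rule, so a late increase may not reach the second arm

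*Protocol*

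**What the plan says.** The protocol describes the range in these places.

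- **Fixed for both arms.** After the third night, Section 4.2.2 narrows the range to P95 ± 2 cmH2O and says "This range will be used for the remainder of both arms of the study". The synopsis agrees: "This same pressure range will be used during the second arm for each patient".
- **Adjustable in the first arm.** The next paragraph of Section 4.2.2 begins "During usage in the first arm, P95 and AHI will be monitored to assure that the patient is receiving proper therapy" and continues "If P95 is near the upper limit and the AHI is above 5 events per hour, the range will be bumped up by 2" cmH2O. It does not define how close 'near' is, or say how often the range may be raised or up to which night.
- **Carried over by 'bulk'.** At the switch, Section 4.2.2 has the coordinator set the second mode "employing the same pressure range as was used in the bulk of the first arm". Section 4.2.3 makes the second-arm procedure the same as the first, with one exception: "the device pressure range will be retained at the same settings that were present during the bulk of the first arm".
- **Opening nights.** The synopsis says "In both the APAP and TPAP arms, participants will have their therapy set to" 5-20 cmH2O for three nights. Section 4.2.1 places that setting at the initial equipment set-up.

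**The concern.** These are instructions that a coordinator carries out remotely, so they should give one answer for each patient. They do not. A range that may be raised is not the one kept for the rest of both arms. Once it has been raised, 'bulk' does not say which of the two settings goes forward. Two coordinators could each follow the text and give the same patient different second-arm settings.

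There are two consequences. First, what a patient receives in the second arm can depend on when in the first arm the trigger was met. Second, the range can respond to P95 and AHI in the first period, while no such response is written for the second. Residual AHI and P95 are secondary endpoints and are tied directly to the range in force.

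**Working it through.** The protocol gives no figure of its own on this point. The check is to follow the text for one patient and count nights.

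**Inputs.** Each arm lasts 6 weeks, or 42 nights (synopsis). The range is narrowed after three nights at 5-20 cmH2O (synopsis; Section 4.2.2). Let k be the first night on the raised range.

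**Reading A: 'bulk' is the range used on most nights after the three opening nights.** This is an assumption.

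- Nights on the first narrowed range (night 4 to night k − 1): k − 4.
- Nights on the raised range (night k to night 42): 43 − k.
- The raised range is carried over if 43 − k > k − 4, that is, if k < 23.5.

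| First raised night | Narrowed range | Raised range | Carried into arm 2 |
|---|---|---|---|
| 14 | 10 | 29 | raised |
| 22 | 18 | 21 | raised |
| 23 | 19 | 20 | raised |
| 24 | 20 | 19 | the range before the increase |
| 28 | 24 | 15 | the range before the increase |
| 35 | 31 | 8 | the range before the increase |

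**Reading B: 'bulk' is more than half of all 42 nights, so more than 21.** The raised range qualifies if 43 − k > 21, so k ≤ 21. The earlier range qualifies if k − 4 > 21, so k ≥ 26. For an increase on nights 22 to 25 neither qualifies, and the rule gives no answer.

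**Length of the opening phase.** Section 4.2.2 ties the narrowing to a third night with at least 5 hours of use, which need not be calendar night 3. With m opening nights, Reading A carries over the raised range if 43 − k > k − 1 − m, so k < 22 + m/2. The cutoff moves later as m grows. Night 24 is therefore one case, not a figure fixed by the protocol.

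**Adjustment rules by period.** Section 4.2.2 places the trigger in the first arm. Section 4.2.3 repeats the procedure but exempts the range, which is retained. Monitoring may continue in the second arm, but no range response is written for it.

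**The case against.** The strongest reply is that this is loose drafting: a general rule followed by a specific exception, with 'bulk' meaning only the narrowed range as opposed to the opening nights at 5-20 cmH2O. That reading is natural and may be what was meant. It works for a patient whose range never changes. Once the range has been raised there are two narrowed settings, and the text still does not choose between them.

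Several stronger inferences are tempting, but the protocol does not support them.

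- *That inheriting the range from the first therapy is itself a flaw.* Using the same limits for both therapies within a patient is a defensible control.
- *That the usage comparison is biased by sequence.* With a period-adjusted analysis, the bias is half the difference between the shift in second-period TPAP usage and the shift in second-period APAP usage. Equal shifts cancel. For scale only, an assumed difference of 0.1 to 0.5 h would move the estimate by 0.05 to 0.25 h, against the assumed treatment difference of 0.5 h. Nothing in the protocol shows that such a difference exists, or in which direction.
- *That exactly 18 of 36 patients would use a TPAP-derived range under APAP.* This is only an expected split, because Section 7.2 uses an unrestricted odd/even draw. The synopsis also gives 32 participants, not 36.
- *That the opening 5-20 cmH2O nights are a firm contradiction.* The synopsis itself carries the same range into the second arm, and Section 4.2.1 ties 5-20 to the initial set-up. One clarifying phrase is enough.
- *That a raised AHI in the second arm has no response at all.* The contact schedule continues, and Section 5.7 lets the Investigator change management after a clinically significant finding. Only a stated range response is absent.

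**Conclusion.** The conflict in the text is real. The range is called fixed, is then adjustable in one arm, and is carried over by a term that does not identify a setting. Taken literally, a patient whose range was raised late in the first arm starts the second arm on the range that had triggered the increase. The cutoff is night 24 of 42 if there are three opening nights and 'bulk' means most of the remaining nights. It moves under other readings.

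The consequence for interpretation is limited to what the text supports. The periods run under different adjustment rules, which bears directly on AHI and P95. The number of patients affected is unknown, because the protocol does not say how often the trigger would be met. Bias in the primary usage comparison is a further inference that the protocol neither establishes nor sizes. No view is taken on which pressure rule is right.

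**What to change.** Reconcile the synopsis with Sections 4.2.2 and 4.2.3 so that they state once:

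1. whether the range is fixed or adjustable after it is narrowed;
2. whether the P95/AHI check, and any range response to it, applies in both arms or in neither, with 'near the limit' defined if the check stays;
3. whether the opening 5-20 cmH2O nights apply to the first period only;
4. which dated setting is carried into the second arm, in place of 'bulk'.

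The clinical choice in each case is the sponsor's.

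Also record the range in force by date, so that AHI and P95 can be read by sequence as well as by therapy. Section 6.1 lists usage, P95, leak and AHI as the nightly data, but not the settings. The synopsis limits P95 collection to the CPAP/APAP arm, while Sections 4.2.2 and 6.1 do not. That should be aligned in the same edit.

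The cost is a protocol wording change and a small amount of extra record keeping.
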